### **5.3. Treatment Response**

The treatment response can be following categories: Complete Remission (CR), Complete Remission with incomplete hematologic recovery (CRi), Morphologic Leukemia-Free State (MLFS), Partial Remission (PR), Stable Disease, Treatment Failure, Progressive Disease (PD), Relapse.

### **5.4. Minimal Residual Disease (MRD)**

MRD will be detected by using PCR or flow cytometry. The results will be reported in negative (MRD-) or positive (MRD). To achieve MRD negative is one of goals for the treatment.

### **5.5. Hematologic recovery**

Hematologic recovery or peripheral blood count recovery is Absolute Neutrophil Count (ANC)  $\geq$  1000/mm^3 and platelets  $\geq$  100,000/mm^3

### **5.6. Event-Free Survival (EFS)**

EFS is defined as time from study randomization to the date of induction treatment failure, relapse after CRc or to death from any cause after CRc, whichever comes first. For patients alive without induction treatment failure or relapse after CRc, EFS will be censored at the date of the last disease evaluation.

The main analysis of EFS is to set the event date for induction treatment failure on day 1 of randomization.

### **5.7. Overall Survival (OS)**

OS is defined as the duration of time from start of treatment to time of death.

## **6. SAFETY MEASUREMENTS**

Safety will be evaluated by

- Adverse events
- Concomitant medications and procedures
- Clinical laboratory tests,
- Physical examination findings,
- Vital signs measurements, and
- Electrocardiogram

## 6.1. Adverse Events

**Adverse Event (AE)** is defined as any new untoward medical occurrence or worsening of a pre-existing medical condition in a patient administered a medicinal product in a clinical investigation and which does not necessarily have a causal relationship with this treatment. An AE can therefore be any unfavorable and unintended sign (e.g., including an abnormal laboratory finding), symptom, or disease temporally associated with the use of a product (investigational or marketed), whether considered related to the product (investigational or marketed).

After either informed consent, but prior to initiation of study treatment (cytarabine or daunorubicin), only AEs/SAEs caused by a protocol-mandated intervention not considered standard of care will be collected (e.g., SAEs related to invasive procedures such as biopsies). After the initiation of study treatment, any changes from baseline which meet (CTCAE V 5.0) Grade  $\geq 3$  AEs and SAEs must be recorded on the appropriate page of the electronic Case Report Form (eCRF). In addition, AEs less than Grade 3 that meet dose interruption, reduction or discontinuation must also be recorded, including:  $\geq$  Grade 2 pancreatitis, QTc interval, PRES, cerebellar toxicity of any grade, creatinine  $>2$  mg/dL and direct or total bilirubin  $\geq 2$  mg/dL.

The following information should be included for all AEs: date of onset and resolution, severity of the event; the investigator's opinion of the relationship to study drug; intervention or treatment required for the AE; action taken with study drug; cause of the event; and information regarding resolution/outcome.

The categories and definitions of severity used for clinical trials AEs are defined in the NCI's Common Terminology Criteria (CTCAE) V5.0 (<http://www.ctep.cancer.gov>).

Categories 'definite', 'probable' and 'possible' are considered study drug related. Categories 'unlikely' and 'unrelated' are considered not study drug related.

AEs related to cytarabine, daunorubicin, gilteritinib or midostaurin should be followed for 30 days after last dose of study therapy until  $\leq$  grade 1 or stabilization. Any AE's (serious or not) that occur more than 30 days after the last dose of study therapy but that are deemed to be at least possibly related to study therapy shall be reported.

All laboratory results required by protocol will be recorded directly on the laboratory eCRF pages.

Only clinically significant laboratory abnormalities that require active management will be recorded as AEs or SAEs on the eCRF (e.g., abnormalities that require study drug dose delay, discontinuation of study treatment, more-frequent follow-up assessments, further diagnostic investigation, etc.).

## 6.2. Concomitant Medications and Procedures

Concomitant medications and procedures will be collected during the trial and recorded in the CRF page.

### **6.3. Clinical Laboratory Assessments**

Clinical laboratory tests will be collected at screening, prior cycles of treatments, twice weekly during induction, weekly in consolidation, and at end of treatment.

### **6.4. Physical Examination and Medical History**

Medical history will be collected at screening. Physical examination findings will be collected at screening, prior treatment cycles, daily after induction treatment or weekly after consolidation, and at end of treatment.

### **6.5. Electrocardiogram**

Perform 12-lead ECG in triplicate (3 separate ECGs recorded at least 5 minutes apart) following a 10- minute resting period prior to treatment. The mean QTcF of the triplicate ECG tracings will be used for final treatment decisions and AE reporting.

## **7. GENERAL STATISTICAL CONSIDERATIONS**

This section will go into detail about the statistical approaches and methodology for this study analysis. Statistical analysis and programming of tables and listings will be conducted by QDS, using SAS® Release 9.4 (SAS Institute Inc., Cary, North Carolina, USA).

### **7.1. Methodology**

In general, listings will be presented by patient. Tables will be summarized and presented by treatment arm in specific analysis populations.

The results of this study will be reported using summary tables, figures, and data listings. Continuous variables will be summarized using mean, SD, median, minimum, and maximum. Categorical variables will be summarized by presenting the number (frequency) and percentage in each treatment arm.

### **7.2. Handling of Repeat, Dropouts or Missing Data**

All attempts will be made to prevent any missing values. Missing or invalid data will be treated as missing, not imputed.

If collected AE onset date is missing, then the Treatment-emergent AE (TEAE) is assumed. If the AE onset date is partial, a conservative approach will be applied. The date will be compared as far as possible with the date of first dose date. If missed date and the same month, then the TEAE is assigned. If only onset year available and the same year of first dose date, then TEAE is assigned. If the relationship with study medication is missing, then related is assigned.

If any post-dose safety data is repeated, the measurement taken first at the visit in question will be used in the analysis.

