**Calculation of QTc interval using the Fridericia formula:**  
[https://qxmd.com/calculate/calculator\\_48/ecg-corrected-qt](https://qxmd.com/calculate/calculator_48/ecg-corrected-qt)
- 14 Perform 12-lead ECG in triplicate (3 separate ECGs recorded at least 5 minutes apart) following a 10 minute resting period prior to gilteritinib or midostaurin administration (ECG within 1 hour of dosing preferred). The mean QTcF of the triplicate ECG tracings will be used for final treatment decisions and AE reporting. If the mean of the triplicate QTcF is >500 msec, then triplicate ECGs will be repeated (within 2 hours). If the repeat ECGs confirm a mean QTcF >500 msec, refer to Section 6.1.2 and Section 6.1.3 for further guidance on treatment decision. In addition, on Cycle 1, Day 15 if QTcF is increased >30 msec over screening, repeat ECG on Day 16 and refer to Section 6.1.2 for further guidance on treatment decision.
- Induction (First Induction)**  
Day 8, Day 15 and Day 21
- Second Induction and Consolidation**  
Day 8 of each cycle
- See footnote 13 for Calculation of QTc interval using the Fridericia formula.**
- 15 Perform 12-lead ECG in triplicate (3 separate ECGs recorded at least 5 minutes apart) following a 10 minute resting period.  

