### **7.4.1. Safety Population**

Safety population is used for safety analysis. The safety population is defined as all patients treated with at least one dose of study medication during the study. All safety data collected up to the end of the study are included in the safety analysis.

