### **7.5.7. Clinical Laboratory Data**

The Lab shift from baseline table will be displayed by treatment arm at End of Induction, End of Consolidation and End of Study for each laboratory test.

Laboratory results will be graded by CTCAE (v5.0) and summary the maximum grade in each lab category.

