### **7.5.9. ECG Data**

ECG data collected value and change from baseline will be summarized by treatment cycle and displayed by treatment arm and overall treatment group. For the triplicate measurements in a timepoint, the average of the 3 records will be represented for that timepoint value in analysis.

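### SAP 7.2 keeps only the first of repeated safety measurements at a visit and makes no exception for the maximum laboratory grade in SAP 7.5.7, so that maximum may be understated

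*SAP*

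**What the plan says.** SAP 7.2 sets a single selection rule for repeat measurements: "If any post-dose safety data is repeated, the measurement taken first at the visit in question will be used in the analysis". It lists no exception, and the SAP defines neither a visit nor a repeat.

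SAP 7.5.7 plans two laboratory outputs. One is tied to time points: "The Lab shift from baseline table will be displayed by treatment arm at End of Induction, End of Consolidation and End of Study". The other is a worst-case summary: "Laboratory results will be graded by CTCAE (v5.0) and summary the maximum grade in each lab category". The section does not say which values enter the maximum.

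SAP 6.3 gives the laboratory frequency as "twice weekly during induction, weekly in consolidation". In the Protocol Section 10 table, chemistry and liver tests stand in the weekly column of induction. Footnote 8 makes those draws twice weekly, and footnote 4 allows further tests on clinical grounds.

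SAP 7.4.1 adds a general statement: "All safety data collected up to the end of the study are included in the safety analysis". It does not refer to 7.2, and 7.2 does not refer to it.

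**The concern.** A rule of one value per visit suits a table that needs one value per visit, such as a shift table. It does not suit a maximum, which should be taken over everything observed. A programmer who follows 7.2 as written would select first values and then take the highest grade among them. A patient whose first sample on a day is grade 2 and whose repeat is grade 3 would be reported as grade 2, unless another visit's first value reached grade 3.

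At stake is the laboratory maximum-grade table, which matters for three reasons:

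- It does not depend on the investigator's view of causality.
- It is the main source for grade 1–2 laboratory maxima, because Protocol 8.1 generally asks for adverse-event entries only from grade 3, with listed exceptions.
- The SAP 7.5.6 table of worst adverse-event grade per patient covers non-hematological events only, so worst hematological grades lean more on the laboratory summary.

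Assessing toxicity in each arm is a secondary objective, and Protocol 11.1.9.3 lists raised transaminases among the gilteritinib risks.

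**Working it through.** The documents state no figure on this point, so there is nothing to reproduce. The check is a comparison of passages, one inequality, and an illustration on assumed inputs.

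**1. Do other sections remove the conflict?** SAP 7.2 is the specific rule on which value to use. SAP 7.5.7 asks for a maximum and is silent on selection. SAP 7.4.1 describes the scope of safety data in general terms. A general scope statement does not clearly override a specific selection rule, so on a literal reading 7.2 governs the input to the maximum.

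**2. Direction.** The first values are a subset of all values, so max(first values) ≤ max(all values). The two are equal when the first value at the visit is the worst, or when another visit's first value reaches the same grade. Otherwise the reported maximum is too low. It can never be too high.

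**3. Size, on assumptions.** None of these inputs is in the documents:

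- k = number of collection days. Two draws a week for four weeks gives 2 × 4 = 8. Two a week up to Day 60 gives 60 ÷ 3.5 ≈ 17.
- p = chance that a day's first value is grade 3 or higher: 0.01 or 0.03.
- r = share of collection days with a repeat: 0.02 or 0.10.
- q = chance that the repeat is grade 3 or higher when the first value was not: 0, 0.01 or 0.05.

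With days treated as independent, the share of patients whose maximum is grade 3 or higher is

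- first values only: 1 − (1 − p)^k
- all values: 1 − [(1 − p)(1 − r·q)]^k

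Worked example, k = 17, p = 0.01, r = 0.10, q = 0.05: first values only give 1 − 0.99^17 = 15.7%. All values give 1 − (0.99 × 0.995)^17 = 22.6%. The gap is 6.9 points.

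| k | p | First only | All: q = 0 | All: r = 0.02, q = 0.01 | All: r = 0.10, q = 0.01 | All: r = 0.10, q = 0.05 |
|---|---|---|---|---|---|---|
| 8 | 0.01 | 7.7% | 7.7% | 7.9% | 8.5% | 11.4% |
| 8 | 0.03 | 21.6% | 21.6% | 21.8% | 22.3% | 24.7% |
| 17 | 0.01 | 15.7% | 15.7% | 16.0% | 17.1% | 22.6% |
| 17 | 0.03 | 40.4% | 40.4% | 40.6% | 41.4% | 45.3% |

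The understatement runs from 0 to 6.9 points. Independence probably exaggerates it, because an abnormality that lasts to the next visit would be caught by that visit's first value.

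**4. Which outputs are touched?** The shift tables need one value per time point, so the rule is reasonable there. Adverse-event grades are reported by investigators and do not pass through 7.2. That leaves the maximum-grade laboratory summary.

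**The case against.** The strongest reply is that the SAP can be read coherently. SAP 7.4.1 includes all safety data, 7.5.7 asks expressly for a maximum, and 7.2 has a natural home in the shift tables. A sensible programmer might do the right thing. That is fair, but it relies on the programmer departing from a rule worded to cover any post-dose safety data. The text should not need that.

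It is also fair that nothing in the documents shows repeats to be worse than first values. A repeat ordered to check an abnormal result may well be lower, and then nothing is lost.

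Three stronger readings are tempting, and the documents do not support them:

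- **That the trial's toxicity results are understated.** Protocol 12.2.2 defines toxicity through adverse events judged related to treatment, which 7.2 does not filter. Protocol 8.1 has grade 3 or higher laboratory abnormalities recorded as adverse events or under the underlying diagnosis, and it lists creatinine and bilirubin thresholds that must be recorded below grade 3. SAP 6.1 words this recording more narrowly, as abnormalities that matter clinically and are actively managed, but the route remains separate from 7.2.
- **That half the induction chemistry is discarded.** This needs a visit to mean a calendar week, so that the planned second draw becomes a repeat. Two scheduled draws are more naturally two assessments. Because the terms are undefined, one clause should close off the other reading.
- **That high QTcF values are lost in the same way.** ECG triplicates have their own rule: "For the triplicate measurements in a timepoint, the average of the 3 records will be represented for that timepoint value in analysis". The protocol's repeat is triggered by a high first result: "If the mean of the triplicate QTcF is >500 msec, then triplicate ECGs will be repeated (within 2 hours". Keeping the first set would keep the triggering value, so this is no example of downward bias.

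**Conclusion.** The point holds for one output. As written, SAP 7.2 can remove a worse same-visit repeat from the maximum CTCAE laboratory grade in SAP 7.5.7, and any resulting error is an understatement. The size cannot be known from the documents. The range of 0 to about 7 points rests entirely on the assumed repeat rates and grade probabilities above and on independence between days, and it is zero if repeats are never worse than first values. The rule applies alike to both arms, and no difference between them is shown. The adverse-event toxicity tables and the primary endpoint are not affected. It is a modest point, but worth correcting because a stated rule can produce a wrong maximum.

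**What to change.** In SAP 7.2, limit the first-measurement rule to summaries that need one value per visit, such as the laboratory shift tables.

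In SAP 7.5.7, add a sentence to this effect: *Maximum CTCAE grade is the worst grade among all post-dose values in the period (induction or consolidation), including scheduled, repeat and unscheduled values; each twice-weekly induction draw is a separate assessment.*

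The cost is a sentence or two and a small change to the programming of one table. Protocol 8.1 already sends protocol-required laboratory results to the laboratory eCRF pages. The sponsor should confirm that tests done on clinical grounds are entered there too. SAP 2.1 provides a running note for changes after finalization, so no new SAP version is needed.

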### 7.3. Endpoints

#### 7.3.1. Primary Endpoint

The primary endpoint of this study is the FLT3 mutation negative (evaluated by polymerase chain reaction [PCR]) Composite Complete Response (CRc) [includes CR and CRi] rate after induction treatment and complete MRD assessment. The cut points used for FLT3 mutation negative are 1% (equivalent to  $10^{-2}$ ) for FLT3-TKD and  $10^{-4}$  for FLT3-ITD.

The final analysis of FLT3 mutation negative CRc rate will be performed after the last patient has completed the induction treatment and all patients have MRD response data available. Patients who drop out prior to MRD response assessment or without MRD assessment will be counted as non-responders in the analysis. The FLT3 mutation negative CRc rate will be compared between gilteritinib and midostaurin arms using Fisher's exact test. All eligible and treated patients will be included into the analysis. Two-sided 90% confidence interval on the difference in the FLT3 mutation negative CRc rate will be provided based on the normal approximation to the difference of two independent binomial proportions with continuity correction.

#### 7.3.2. Secondary Endpoints

The secondary objective endpoints are:

1. The FLT3 mutation negative CR rate of patients with FLT3 mutated AML.
2. The MRD- CRc rate of patients with FLT3 mutated AML
3. The CRc rate of patients with FLT3 mutated AML
4. Event Free Survival (EFS)

The FLT3 mutation negative Complete Response (CR) rate of patients with FLT3 mutated AML who receive gilteritinib will be compared to those who receive midostaurin in addition to standard therapy with cytarabine and daunorubicin during induction. The final analysis of FLT3 mutation negative CR rate will be performed after the last patient has completed the induction treatment and all patients have MRD response data available. Patients who drop out prior to MRD response assessment will be counted as non-responders in the analysis. The FLT3 mutation negative CR rate will be compared between gilteritinib and midostaurin arms using Fisher's exact test. Two-sided 90% confidence interval on the difference in the FLT3 mutation negative CR rate will be provided based on the normal approximation to the difference of two independent binomial proportions with continuity correction.

### 7.4. Analysis Populations

The FLT3 mutated AML adult patients are this study population. There will be a total of 179 patients enrolled into this study.

Patients negative for FLT3 mutated AML will not be eligible to enroll the study and counted as screen failure.

### **7.4.1. Safety Population**

Safety population is used for safety analysis. The safety population is defined as all patients treated with at least one dose of study medication during the study. All safety data collected up to the end of the study are included in the safety analysis.

### **7.4.2. Efficacy Population**

Efficacy population will be all eligible and treated subjects. Ineligible and never started treatment will be excluded from this population. The eligible patients are subjects already pre-screened, enrolled with signed consent and randomized into treatment arms.

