## **7.6. Efficacy Analysis**

All Efficacy analyses are performed for efficacy population.

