### **7.6.6. Event-Free Survival Analysis (EFS)**

EFS is defined as time from study randomization to the date of induction treatment failure,

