## Statistical Analysis Plan

Study code PrE0905

Version Final V3

Date 09 November 2023

relapse after CRc or to death from any cause after CRc, whichever comes first. For patients alive without induction treatment failure or relapse after CRc, EFS will be censored at the date of the last disease evaluation.

The main analysis of EFS is to set the event date for induction treatment failure on day 1 of randomization.

A sensitivity analysis of EFS will be performed where follow-up will be censored at the start of transplantation (if transplant was done before the date of the last disease evaluation).

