### 7.6.7. Overall Survival (OS)

OS is defined as the time between randomization and death from any cause. The censored follow-up time for patients without death information is the date of last contact.

The final analysis of EFS and OS will be performed when the full information of EFS is reached (i.e., 110 events have occurred). Estimates of EFS and OS, including medians and confidence intervals, will be calculated using the Kaplan-Meier method. Comparison of EFS and OS between treatment arms will be conducted using the one-sided stratified log-rank test with FLT3 mutation (TKD vs ITD), FLT3-ITD mutation signal ratio (high  $\geq 0.5$  vs. low  $<0.5$  of FLT3 Wild Type), and NPM1 mutation status, the same stratification factors used in randomization. A multivariate Cox proportional hazards model, stratified on the same factors above, will also be used to assess the treatment effect.

Comparison of EFS and OS between treatment arms will also be conducted in patients with de novo AML, t-AML and AML-MRC separately; and in patients with favorable, intermediate, and adverse risk separately, determined by 2017 ELN risk classification.

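### The SAP drops randomized patients who never start treatment from EFS and OS, although both run from randomization in an open-label trial, and it gives OS two different start dates

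*SAP*

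**What the plan says.** SAP 7.4.2 builds the efficacy population from eligible and treated patients and states: "Ineligible and never started treatment will be excluded from this population". It then describes eligibility this way: "The eligible patients are subjects already pre-screened, enrolled with signed consent and randomized into treatment arms". SAP 7.6 gives the scope: "All Efficacy analyses are performed for efficacy population".

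That scope takes in both time-to-event endpoints. In SAP 7.6.6, "EFS is defined as time from study randomization to the date of induction treatment failure", with the later events being "relapse after CRc or to death from any cause after CRc, whichever comes first". In SAP 7.6.7, "OS is defined as the time between randomization and death from any cause", which agrees with protocol 12.2.2. SAP 5.7 differs: "OS is defined as the duration of time from start of treatment to time of death".

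Protocol 12.2.1 restricts the primary rate to eligible, treated patients. Protocol 12.2.2 names no analysis population for EFS or OS, though it sizes EFS on about 170 eligible patients. Assignment is not blinded (protocol 4.4, SAP 4.3). SAP 8 declares no changes from the protocol's analyses.

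**The concern.** Randomization makes the arms comparable at the moment of assignment. Whether a patient then starts treatment is settled afterwards, with the arm known to patient and investigator. Removing non-starters from an endpoint counted from randomization can therefore unbalance the arms if non-starting depends on the arm and on prognosis. At stake are the EFS and OS comparisons and the EFS futility look in SAP 7.7, which can end the study.

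Three wording problems add to this.

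- **Two OS start dates.** SAP 2.1 says the SAP supersedes the protocol's statistical section, so the protocol does not settle the conflict. 7+3 may begin before randomization, so the two dates can differ in either direction. A patient who never starts has no OS start date at all under SAP 5.7.
- **Eligible.** Read literally, the second sentence quoted from SAP 7.4.2 makes every randomized patient eligible, yet the section also excludes ineligible patients.
- **Treated.** The term is not defined for efficacy.

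**Working it through.** **1. The plan's own figures.** These reproduce, so the issue is not sample size.
- Primary: exact one-sided Fisher test, alpha 0.05, 85 per arm, 40% vs 60%: power 80.6% (stated 80%). Inflation: 170/0.95 = 179.
- EFS: hazard ratio 0.62, one-sided 0.05. The Schoenfeld formula gives 109 events and the Freedman formula 113 (stated about 110). Power at 110 events is 80.6%.
- Expected EFS events under the stated cure model (25% cured, 6-month median in the rest, 7 patients a month, 2 years of follow-up): 110.2 in 170 patients, about 116 in 179. Power at 116 events is 82.4%.

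**2. Who is removed, and does anything restore them?** SAP 7.4.2 with 7.6 removes never-started patients from all efficacy analyses. Two sensitivity analyses in the SAP alter the set or the censoring. SAP 7.6.1 narrows to patients with an MRD assessment, and SAP 7.6.6 censors EFS at transplant. Neither brings anyone back.

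**3. What does treated mean?** Protocol 5.2.1 counts Day 1 from the first dose of induction chemotherapy, and SAP 6.1 equates study treatment with cytarabine or daunorubicin. Any 7+3 dose is therefore the natural reading. Only the treatment-emergent AE definition in SAP 7.5.6 points to the FLT3 inhibitor, planned from Day 8. SAP 13 explains that this definition was changed because 7+3 can precede randomization.

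**4. Size for OS.** The documents give no non-start count, so the counts below are assumptions. Take 90 per arm, equal true 2-year survival of 50% (45 alive), and 1 to 3 non-starters in one arm only. Approximate HR = ln(new survival)/ln(true survival).

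| Dropped from one arm | That arm's 2-year survival | Approximate HR |
|---|---|---|
| 1, died | 45/89 = 50.6% | 0.98 |
| 3, died | 45/87 = 51.7% | 0.95 |
| 1, alive | 44/89 = 49.4% | 1.02 |
| 3, alive | 42/87 = 48.3% | 1.05 |

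For true survival of 30% to 60% the ranges are 0.99-0.93 and 1.01-1.07.

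**5. Worst-case type I error.** Simulated unstratified one-sided log-rank test, exponential survival, 90 per arm, uniform accrual over 2.1 years plus 2 years of follow-up, 40,000 runs. Those dropped are the arm's earliest deaths.

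| Dropped | From Arm A | From Arm B |
|---|---|---|
| 0 | 5.1% | 5.1% |
| 1 | 6.2% | 4.2% |
| 2 | 7.3% | 3.5% |
| 3 | 8.9% | 2.9% |

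Three dropped at random leave it at 5.1%. One early death dropped from each arm gives 5.2% (separate run of 10,000).

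**6. Primary rate, for the sensitivity analysis only.** Exact one-sided Fisher test on treated patients, 85 eligible per arm, true rate 40% among all eligible in both arms, non-starters being non-responders.
- No non-starters: type I error 3.6%.
- Arm A only, 2% (rate among treated 0.40/0.98 = 40.8%, 83 vs 85 patients): 4.7%.
- Arm A only, 5% (0.40/0.95 = 42.1%, 81 vs 85): 6.9%.
- Arm B only, 2% and 5%: 2.7% and 1.9%.
- 5% in both arms: 3.4%.

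Power at 5% non-start in both arms is 77.5% treated-only (81 per arm, 60% vs 40%). It is 76.7% with non-starters as non-responders (85 per arm, 0.95 x 60% = 57% vs 0.95 x 40% = 38%). At 2% both are 79.1%.

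**The case against.** The strongest reply is that the practical effect may be negligible. Under the 7+3 reading, patients who began chemotherapy before randomization already count as treated. The others are due the same chemotherapy in both arms within 3 days (protocol 4.4 and 5.2.1), and the documents name no arm-specific reason for not starting it. Every error rate above 5% requires losses concentrated in one arm and tied to outcome, apart from the 5.2% with one early death dropped per arm, which is within simulation error of the baseline. This stands, and it sets the size of the point.

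Protocol 12.2.2 is also not wholly silent: sizing EFS on eligible patients points to an eligible basis. That stands too, and is why the main set proposed below is eligible randomized patients rather than everyone randomized.

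The OS conflict is partly a wording slip. SAP 7.6.7 matches the protocol, and for patients starting 7+3 after randomization the gap is at most about 3 days. It still needs correcting, because one SAP should not define OS twice.

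Tables are in a separate template not available here, so the absence of a restoring analysis is shown for the SAP text only.

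Stronger readings that a reader might infer are not supported:
- **That the plan favours gilteritinib, or that its error rate is 9%.** No non-start rate or arm imbalance is given, and losses from Arm B push the error rate down.
- **That many patients are lost because treated means the Day 8 inhibitor.** Supply does differ by arm (protocol 11.1.6 and 11.2) and access delays are foreseen (5.2.1), but this reading rests only on the AE definition. Five deaths dropped, a loss more plausible under that reading, would give 45/85 = 52.9% (HR 0.92).
- **That living never-induced patients are miscounted in EFS.** The existing rule covers them: "For patients alive without induction treatment failure or relapse after CRc, EFS will be censored at the date of the last disease evaluation".
- **That the primary population departs from the protocol.** It does not; 12.2.1 sets it.

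**Conclusion.** The point holds on the text and should be corrected. The exclusion of never-started patients from EFS and OS is the SAP's own extension of a rule the protocol states only for the primary rate. It selects on an event after open-label assignment, and no stated analysis undoes it. The OS start contradiction is definite.

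Size and direction are unknown. With 1 to 3 non-starters in one arm, the hazard ratio moves by roughly 2% to 5% at 50% two-year survival. One-sided type I error lies between about 3% and 9% only if those patients are that arm's earliest deaths. The effect is likely small if treated means any 7+3 dose, and absent if losses are balanced or unrelated to prognosis. These figures rest on assumed counts, 90 per arm and exponential survival.

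One EFS question stays open. The definition names death after CRc, while protocol 9.6 lists deaths before completion of therapy under treatment failure, which the main analysis dates on day 1. A reader might conclude that every death without CRc should be an event at the date of death. The documents do not support that default, which would re-date induction deaths of treated patients.

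**What to change.** 1. Analyse EFS and OS by assigned arm in all eligible randomized patients regardless of treatment start, with eligibility judged on pre-randomization criteria only. Use this set for the 110-event trigger and the EFS futility look. Show all randomized patients as a sensitivity analysis where follow-up exists.
2. Keep the eligible-and-treated set for the primary rate, as protocol 12.2.1 has it, and add a sensitivity analysis counting never-treated eligible patients as non-responders.
3. Correct SAP 5.7 so that OS starts at randomization. Define treated as at least one dose of any induction drug, including 7+3 begun before randomization. Remove the sentence in SAP 7.4.2 that makes every randomized patient eligible.
4. Reconcile the EFS definition with protocol 9.6 on deaths without CRc, without imposing a new default date.

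**Cost.** SAP wording and one extra set of tables; no change in sample size, since the EFS sizing already counts eligible patients. The non-responder analysis has 0.8 points less power at an assumed 5% non-start (77.5% - 76.7%) and no loss at 2%. SAP 7.5.1 already tabulates disposition by arm, and protocol 14.7 has the reason for not starting recorded. Living untreated patients will add little EFS information, because they are censored at their last disease evaluation; the gain is mainly in OS. Protocol 7.2 covers untreated patients who are eligible, and 14.7 covers any registered untreated patient, but in describing the data kept for them neither spells out long-term survival. Its availability must be checked first, above all for the ineligible patients in the all-randomized analysis (planned allowance 179 - 170 = 9).
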